4.1. Inclusion Criteria

Candidates for this study must meet **all** of the following inclusion criteria:

1. Participant is male or female and at least 18 years of age
2. HSV-2 seropositive by the UW Western blot or Alegria assay
3. History of recurrent genital herpes with at least 3 recurrences in the last year or, if currently on suppressive/ prophylactic therapy, prior to starting the therapy (antiviral therapy has to be stopped at least 7 days prior to initiation of the trial product).

4. General good health at the discretion of the investigator.
5. Willing to not use any topical genital therapy aside from the study device for the duration of the trial.
6. Willing to not use any systemic anti HSV therapy during the entire study starting 7 days prior to baseline.
7. Willing to obtain 2 swabs from external-genital areas once daily for the duration of the trial.
8. Willing to keep a daily trial diary during the treatment period.
9. Negative pregnancy test for women at screening.
10. Willing to use contraceptives for the duration of the study.
11. Subject must be willing and able (in the opinion of the investigator) to understand the patient information and informed consent form and to comply with the clinical trial protocol and procedures.
12. Subject must be willing to give written informed consent.

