5.2.2. Participant Screening - Visit 0-1

The screening of potential participants will be conducted by one or more study team members. The site research team will be responsible for ensuring and reporting screening of men and women for study eligibility. Cumulative screening and enrollment logs will be maintained by research sites. Reasons for screen failures will be documented in study logs.

All anti-viral therapies shall be stopped minimally 7 days prior to Visit 1.

Women that are more than 1 year post-menopausal will be considered as having no child bearing potential, and the pregnancy test and use of contraceptives is not applicable for them.

Table 2 lists the schedule of events for participants from the initial screening and baseline measures through their bi-weekly follow-up visits. These measures are more fully described in the subsequent sections.

Table 2. Schedule of Events

Activity	Treatment Period				
	Screening	Visit 1	FUP call	Visit 2	Visit 3
Informed Consent	X				
Review Inclusion/Exclusion Criteria	X				
Medical History (including HSV history)	X				
Interim History (including HSV history)		X		X	X
Targeted Physical Exam (including external genital exam)	X	X*		X*	X*
HSV serology	X				
Urine pregnancy test	X				
Provide Study Device and/or training		X	X	X	
Review device use adherence				X	X
AE assessment				→	
User Questionnaire					X
Daily Swab Collection & Diary				→	

* for women possibly including internal genital exam if symptomatic

The following screening data will be collected for all study subjects prior to enrollment to assess possible eligibility:

- Medical history, standard of care physical examination, including external genital exam

A subject will be considered as "enrolled", once (s)he has signed the Informed Consent. Study

specific data will not be collected for subjects who fail any of the eligibility criteria and do not apply the study product; these subjects will be recorded on a Screening Log where the reason for screening failure will be documented.

5.2.3. Treatment start - Visit 1

Once participant's eligibility is confirmed, i.e. HSV-2 serology is positive, select assessments and laboratory tests will be done prior to document baseline status. These include:

- Physical examination, including a genital examination that for women may include an internal genital examination if symptomatic;
- (Interim) medical history;
- Urine pregnancy test;
- Adverse Events assessment

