Appendix 4. Participant Diary

Day of the month	1	2	3	4	5	6	7	8	9	10
Time Skin Swab Collected										
Time VIBLOK Swab Collected										
Time in case of genital area shaved										
Time in case of genital area waxed										
Time in case of other hair removal										
Specify other hair removal method if applicable										
Anti-HSV medication taken										
Symptoms										
No Symptoms										
Itching, burning, tingling										
Lesions (sores, blisters, ulcers, crusts)										
Other (describe below)										
Lesion Locations										
Genital (Men: penis, scrotum; Women: vagina, labia, vulva, groin, pubis)										
Rectal (perineum, perianal)										
Buttock										
Other: _____										

Day of the month		11	12	13	14	15	16	17	18	19	20
Time Skin Swab Collected											
Time VIBLOK Swab Collected											
Time in case of genital area shaved											
Time in case of genital area waxed											
Time in case of other hair removal											
Specify other hair removal method if applicable											
Anti-HSV medication taken											
Symptoms											
No Symptoms											
Itching, burning, tingling											
Lesions (sores, blisters, ulcers, crusts)											
Other (describe below)											
Lesion Locations											
Genital (Men: penis, scrotum; Women: vagina, labia, vulva, groin, pubis)											
Rectal (perineum, perianal)											
Buttock											
Other: _____											

CLJI WORLDWIDE
 VIBLOK SAfety and perFormancE Trial Protocol
 Date 01/MAY/2017

Day of the month	21	22	23	24	25	26	27	28	29	30	31
Time Skin Swab Collected											
Time VIBLOK Swab Collected											
Time in case of genital area shaved											
Time in case of genital area waxed											
Time in case of other hair removal											
Specify other hair removal method if applicable											
Anti-HSV medication taken											
Symptoms											
No Symptoms											
Itching, burning, tingling											
Lesions (sores, blisters, ulcers, crusts)											
Other (describe below)											
Lesion Locations											
Genital (Men: penis, scrotum; Women: vagina, labia, vulva, groin, pubis)											
Rectal (perineum, perianal)											
Buttock											
Other: _____											

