### 3.4 Demographics and Other Baseline Characteristics

The critical demographic and baseline characteristics of the participants, as well as other factors arising during the study that could affect response, will be displayed by use of tables. The data for the All Enrolled Set will be given first followed by data on the As Treated Population, Per Protocol Population and Safety Analysis Set.

The variables, assessed at the screening visit and at Visit 1, displayed will include:

- demographic variables
  - Age (years)
  - Gender (Male / Female)
  - Race/Ethnic Origin (Participant chose not to share this data / African, American or Black / Asian / Caucasian / Hispanic or Latina / Other race/ethnic origin)
- HSV Serology
  - Units HSV-2 IgG antibody (aU/ml)
  - Units HSV-2 IgG antibody (Negative / Positive / Borderline)
  - Units HSV-1 IgG antibody (aU/ml)
  - Units HSV-1 IgG antibody (Negative / Positive / Borderline)
  - Units HSV- IgM antibody (Negative / Positive / Borderline)
  - Overall result of the Western blot or Allegria Essay test (HSV2 positive and HSV1 negative / HSV2 positive and HSV1 positive / HSV2 negative and HSV1 positive / HSV2 negative and HSV1 negative / HSV positive but origin HSV1 or HSV2 unclear)
- Anti-Viral therapy
  - Current use of any anti-viral therapy at screening (Yes / No)
  - Did the participant stop with any anti-viral therapy recently at screening? (Yes / No)
  - Has anti-Viral therapy been stopped at least 7 days ago at Visit 1? (Yes / No (delay visit 1 or withdraw participant))
- Medical History (general)
  - Does the participant have hypertension? (No/Controlled / Uncontrolled)
  - Does the participant diabetes? (No/ Type 1 / Type 2)
  - Does the participant have cardiac disease? (Yes / No)
  - Is the participant HIV positive? (Yes / No / Unknown)
  - Does the participant have any known allergies? (No / Hay Fever, Dust Mites or Animal Dander / Contact Allergy / (Household) Chemicals / Perfume or Body care products / Latex / Other)
  - Does the participant have a significant autoimmune disease? (No/ Multiple Sclerosis / Myasthenia Gravis / Crohn Disease / Colitis Ulcerosa / Psoriasis / Vitiligo / Lupus Erythematosus / Rheumatoid arthritis /Other)

- Does the participant have any other for the study relevant medical condition? (Yes / No / Unknown)
- Have there been any changes in medical history since previous visit? (Yes / No)

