  - Any new obvious discharge present in the genital, peri-anal, inguinal or pubis area? (Yes / No)
  - Any new other abnormalities in the genital, peri-anal, inguinal or pubis area, NOT related to genital herpes but relevant for the study (at the judgement of the investigator)? (Yes / No)
- The actual targeted Genital Exam will be presented, i.e. the data from the previous visit including the new abnormalities reported at the respective visit.
- Grooming Habits
  - Genital grooming habits (None / Shaving / Waxing / Other)
  - Frequency of performing these extra genital grooming habits (Daily / Weekly / Monthly / Other)

- Did participant change any genital grooming since the screening visit? (Yes / No) The actual grooming habits will be presented, i.e. the data from the previous visit including the changes reported at the respective visit.
- Medication vs Treatment
  - Are there any changes in medication, topical cream or any other product to alleviate genital herpes since previous visit? (Yes / No)
  - Anti HSV medication recorded on the participant's diary
  - Any anti HSV medication taken (Yes / No)
  - The percentage of days anti HSV medication taken in relation to the total number of days of participation.
- Review and collection of participant's diary
  - Did the participant complete the participant diary according procedure? (Yes / No, complete protocol deviation)
- Collection of participant swabs
  - Did the participant collect all required swabs according protocol? (Yes / No, complete protocol deviation)
  - Did the participant complete the swab log according protocol? (Yes / No, complete protocol deviation)
  - Did the participant complete the swab lesion log according protocol? (Yes / No, complete protocol deviation / Not applicable)
- Collection of participant questionnaire
  - Did the participant complete the participant questionnaire? (Yes / No, complete protocol deviation)
- Unscheduled FU information
  - Type of unscheduled follow-up (Phone call / In-Clinic visit)
  - Reason unscheduled follow-up (Genital Herpes outbreak / Other)
  - What type of treatment did the participant start to alleviate the outbreak of genital herpes? (No treatment / Prescription medication / Non Prescription medication / (Topical) cream / Any other treatment). More than one answer allowed.

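### Protocol 5.2.2 and the SAP Visit 1 item put no limit on which antivirals must be stopped, while inclusion criterion 6 covers only systemic anti-HSV therapy; the scope of the washout needs one wording

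*Protocol*

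**What the plan says.** Three places in the protocol deal with stopping antiviral treatment before the cream is used.

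- Section 5.2.2, on screening procedures: "All anti-viral therapies shall be stopped minimally 7 days prior to Visit 1".
- Section 4.1, inclusion criterion 6 (repeated in the synopsis): "Willing to not use any systemic anti HSV therapy during the entire study starting 7 days prior to baseline".
- Section 4.1, inclusion criterion 3 (also in the synopsis), in a parenthesis attached to people on suppressive or prophylactic therapy for genital herpes: "antiviral therapy has to be stopped at least 7 days prior to initiation of the trial product".

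SAP 3.4 lists related variables to be tabulated. One of its two screening items reads "Current use of any anti-viral therapy at screening (Yes / No". The Visit 1 item reads "Has anti-Viral therapy been stopped at least 7 days ago at Visit 1? (Yes / No (delay visit 1 or withdraw participant".

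On who may enter, Protocol 4.2 has no criterion that names antiviral use or another viral infection. Exclusion 1 lists serious conditions, including immunosuppression, but applies only where the investigator expects an effect on outcomes. Exclusion 5 is a general judgement clause.

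**The concern.** The washout is a single instruction to sites, yet its scope depends on the page consulted. Criterion 6 limits it to one class of drug. Section 5.2.2 sets no limit, and the SAP Visit 1 item attaches a consequence to an equally unrestricted term.

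For someone whose only antiviral is for herpes, the passages agree and nothing is at stake. They diverge for someone taking an antiviral for a different infection. A coordinator working from 5.2.2 would have that treatment stopped, or would delay or withdraw the person. A coordinator working from criterion 6 would do neither. The first outcome touches the care of a participant for a condition that is not under study. With up to 6 centres in two countries, different sites could also handle the same person differently.

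**Working it through.** No figure in the plan depends on this point, so the check is a comparison of text.

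**Length and anchor.** All four rules (criterion 3, criterion 6, Protocol 5.2.2, SAP Visit 1 item) use 7 days. The anchors are the start of the product, baseline and Visit 1. Under Protocol 5.2.3 baseline status is documented and the cream is first applied at Visit 1, so these coincide. There is no conflict on timing before treatment.

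**Scope.**

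| Place | Which therapies | Period | Consequence stated |
|---|---|---|---|
| Protocol 4.1, criterion 6 | systemic, anti-HSV | 7 days before baseline to end of study | inclusion criterion |
| Protocol 4.1, criterion 3 | antiviral, in a herpes-suppression clause | 7 days before first use | inclusion criterion |
| Protocol 5.2.2 | all antivirals, no route or target given | 7 days before Visit 1 | none stated |
| SAP 3.4, screening items | any antiviral | current or recent at screening | none (Yes/No) |
| SAP 3.4, Visit 1 item | antiviral, no target given | 7 days before Visit 1 | postpone Visit 1 or withdraw |

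Criterion 6 is explicitly narrow and 5.2.2 is explicitly wide. The word *any* appears only in the screening items, which carry no consequence. The Visit 1 item carries the consequence but uses the bare term, as criterion 3 does.

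**Is the wide term defined as HSV-only?** No passage in either document does so. Elsewhere the SAP names herpes when it means herpes: the treatment items in 3.4 separate genital herpes from other medical conditions and ask about products used to relieve it.

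**Can the two rules meet in one person?** Take someone on an antiviral for an infection other than HSV.

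1. Criterion 6: not engaged, because the drug is not anti-HSV therapy.
2. Exclusions 1 and 5: may apply if the investigator so judges; neither is automatic.
3. Protocol 5.2.2, read literally: the drug must be stopped.
4. SAP Visit 1 item, read literally: if it has not been stopped, Visit 1 is postponed or the person is withdrawn.

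If the investigator does not exclude the person at step 2, step 1 conflicts with steps 3 and 4.

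**The case against.** The best reply is that the meaning is clear from context. Criterion 3 uses the bare term for herpes suppression with the same 7 days, and 5.2.2 can be read as its procedural restatement. The background sections also use the term for herpes drugs such as acyclovir and valacyclovir. This has weight: it makes an HSV-only intent plausible. It does not settle the matter, because 5.2.2 says that all such therapies are covered and nothing tells a site to read it more narrowly.

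It is also fair to say that the SAP Visit 1 item is a baseline variable to be tabulated, not a numbered eligibility criterion. That is correct, although its negative answer works as a gate.

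A reader might infer more than the documents support:

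- **The diary as a rival rule.** The diary row "Anti-HSV medication taken" and its SAP 3.6 summary, "The percentage of days anti HSV medication taken in relation to the total number of days of participation", cover only anti-HSV drugs. But they record use during participation, whereas 5.2.2 governs the period before Visit 1. Other drugs appear in the concomitant medication listings. There is no contradiction here.
- **HIV status as proof of intended entry.** SAP 3.4 tabulates "Is the participant HIV positive? (Yes / No / Unknown". The same list covers diabetes and autoimmune disease, which exclusion 1 names, and the tables start with everyone who consented. Tabulating a condition does not show that people with it are meant to be treated.
- **A shift in the Per Protocol set.** That set requires eligibility and at least 26 days of use. The criteria stand in 4.1 and 4.2, while 5.2.2 is a procedure. Someone withdrawn at Visit 1 before using the cream is in neither the As Treated nor the Per Protocol population. For those who continue, exclusions are settled in the signed Exclusion Memo before database lock. A change in membership is not shown.
- **A head count.** The documents give no rate of non-HSV antiviral use. Even the base is not the 84 enrolled: after the planned 45% screen failure, 84 × (1 − 0.45) = 46.2, or about 46, go on to apply the cream.

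**Conclusion.** The inconsistency is real and narrow. The unrestricted wording of Protocol 5.2.2, echoed in the SAP Visit 1 item, conflicts with the anti-HSV limit in criterion 6 for a person on an antiviral for another infection whom the investigator has not excluded. It rests on a literal reading of 5.2.2; if an HSV-only scope was intended, the defect is that the text does not say so.

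It matters for participant safety and for uniform handling across sites. The number of people affected cannot be estimated from the documents and may be zero. The sample size, the tests and the primary endpoint do not depend on it.

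**What to change.** The sponsor's clinical lead should state one scope for the therapies to be stopped before Visit 1: which agents, by which routes, and over what period. The same words should then appear in inclusion criteria 3 and 6 (synopsis and Section 4.1), in Protocol 5.2.2, and in the screening and Visit 1 antiviral items of SAP 3.4, including the one that triggers postponement or withdrawal. Any case report form item worded in the same way should follow. These passages must be reconciled; this review does not say which scope is right.

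The cost is a wording amendment to the protocol and SAP, with matching form text where needed. No extra participants, visits or tests are involved.

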5.2.4. Treatment - Follow-up call

Two-five days after visit 1, participants will receive a follow-up call by someone from the site research staff to verify that participants have a full understanding and no remaining questions concerning the study procedures, specifically with respect to:

- Swabbing procedures
- Application of the VIBLOK cream
- Completion of the diary

In addition, any AEs will be recorded.

5.2.5. Treatment – Visits 2 and 3

During the treatment periods, participants should:

- Complete their diary daily;

- Take swabs daily, before and 5-60 minutes after applying the cream on the external genitals according to the instructions;
- Visit the clinical trial site every other week

Clinical trial site visits will occur approximately 14 and 28 days after Visit 1.

During the clinic visits the following examinations/ evaluations and procedures will be done by site research staff:

- Adverse Events review;
- Targeted physical examination, including a genital examination that for women may include an internal genital examination if symptomatic;
- (Interim) medical history;
- Review and collection of subject's diary;
- Collection of subject swabs;
- Device accountability;

New trial devices and diary will be provided during Visit 2.

During Visit 3, subjects will be asked to complete a questionnaire regarding the usability of the cream (refer to Appendix 5).

5.2.6. Genital herpes recurrence – Unscheduled visits

If a lesion develops that is consistent with genital herpes, swabs should be obtained from the lesion. Participants who have such a recurrence (i.e., papules, vesicles or pustules, ulcers, or crusts) during the treatment period are requested to contact and return to the clinic for an examination as soon as possible. That examination includes a genital examination, and for women may include an internal genital examination.

In case of a recurrence, participants will be instructed to apply their usual treatment or refer to their treating physician whichever is applicable, in order to receive treatment per standard practice. If the subject is successfully treated within 21 days, and meets the inclusion criteria and none of the exclusion criteria, subject may re-enter the study. The concerning follow-up period is prolonged with the number of days the treatment required. These visits shall be recorded as an unscheduled visit.

In case of a second recurrence, the subject shall exit the study.

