8.1.2. Risks/ Adverse Events associated with VIBLOK cream

In addition to the events listed in the previous section, the additional adverse events listed below are specifically associated with the VIBLOK cream and its application. The lack of data associated with long term VIBLOK usage prevents predicting the incidence of these risks. Additional complications include, but may not be limited to:

- Toxic, hypersensitive or allergic reaction

- Epithelial sensitization

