9.6. Endpoint Analysis

All statistical analyses will be performed by CLJI or a designee. Participant data listings and tabular and graphical presentations of results will be provided. All clinically relevant baseline and follow-up variables will be tabulated. Descriptive statistics will be used for continuous variables (e.g., mean, standard deviation, sample size, minimum, and maximum) and frequency tables or proportions for discrete variables.

Swab samples will be analyzed by a core laboratory for HSV DNA and the mean HSV-2 copy number on HSV-2 DNA positive samples.

Further details of the statistical methods will be provided in the Statistical Analysis Plan.

10. Study Administration

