1. Unwrap 1 sterile swab and hold it by the plastic shaft. Try not to touch the Dacron tip with your hands.

2. Gently put the swab on your labia.
3. Rotate the swab in a full circle. Gently remove the swab from your labia.
4. Rub the same swab from the outer (hairy) edges of your labia to the smooth skin below the vaginal opening, covering the entire area.
5. Rub the swab over the skin between your vagina and anal opening (anus).
6. Rub the swab in a circular motion over your rectal area, covering a radius of about 1.0 cm around the anus.

2/ Closing the vials and labeling:

1. Place the collected swab into the vial with the **green color coded** label.

2. Pull the swab out of the vial 0.5 cm, break (or cut) off the end of the plastic shaft, and discard it in the trash.
3. Securely replace the screw top of the vial.
4. Complete the swab collection log, with the full date (for example: 17-AUG-2015) and time of collection.
5. Place the labeled vial inside the grid box.

3/ Apply VIBLOK

1. Apply one packet of VIBLOK™ evenly and thoroughly to all external genital (including labia and clitoris), pubic, and perianal areas with or without hair.
2. Ensure application from minimally 2 cm outside of the outer (hairy) edges of your labia to the smooth skin below the vaginal opening, covering the entire area, the skin between your vagina and anal opening (anus), and your rectal area, covering a radius of about 2.5 cm around the anus. Apply more than one packet if needed.
3. Wait 5 to 60 minutes.

4/ To collect the **EXTRA GENITAL** swab in the **yellow-labeled** vial after VIBLOK:

1. Repeat the procedure as described under 1/ and 2/ using the vial with the **yellow color coded label**
2. Make sure to rub the swap only in the area where you applied VIBLOK: Keep a distance of at least 1 cm to the outer edges.
3. Use the mirror from your sampling kit if needed.

5/ To collect a **LESION** swab in the **red-labeled** vial:

If you develop a herpes lesion, please rub a separate swab over this area and place the swab in one of the **red-labeled** vials. Do **not** apply VIBLOK when you develop a herpes lesion and call the clinic when you first notice symptoms.

Repeat the procedure as described under 2/.

6/ After collection of the swabs

After you have collected the daily swabs, ensure to

1. thoroughly wash and dry your hands
2. have completed the participant diary

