#### 5.2.2 Display of adverse events

All adverse events occurring after initiation of study treatment (including events likely to be related to the underlying disease or likely to represent concomitant illness) will be displayed in summary tables.

The tables will list each adverse event, the number of participants in whom the event occurred, and the rate of occurrence.

Adverse events will be grouped by the following categories:

- Any event
- Bleeding / Anaemia
- Bowel
- Cardiac
- Malignancies
- Miscellaneous
- Neurological
- Pulmonary
- Renal
- Urogenital
- Vascular
- Genital

- Skin
- Infection
- Trauma
- Other

The analysis of adverse events comprises the following categories:

- Any adverse event
- Any adverse event by consideration
- Adverse events considered to be a toxic reaction
- Adverse events considered to be an allergic reaction
- Adverse events considered to be an infection
- Adverse events considered to be other
- Any adverse event by severity
- Possibly, probably or definitely related to investigational device adverse events
- Possibly, probably or definitely related during application of the investigational device adverse events
- Possibly, probably or definitely related after application of the investigational device adverse events
- Possibly, probably or definitely related to study procedure adverse events
- Adverse events related to a pre-existing / other medical condition
- Adverse event related complications associated with an HSV 2 infection
- Any adverse event
- Recurrence of genital herpes
- Systemic symptoms
- Fever
- Headache
- Malaise
- Myalgia(s)
- Local pain and itching
- Dysuria
- Tender lymphadenopathy
- Unanticipated adverse events
- Adverse events by action taken
- No action taken
- Drug Therapy
- Any
- Prescription
- Non-Prescription
- Surgical intervention or other invasive therapy
- Hospitalization
- Other treatment / procedure
- Withdraw from study due to AE
- Adverse events by outcome
- Resolved
- Resolved with sequelae
- Ongoing
- Ongoing at time of exit
- Unknown / Lost to Follow-up

- Death
- Reportable adverse events

Serious adverse events will only be listed as it will be expected that there will only be very few or no serious adverse event.

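### Lesion swabs are taken at each suspected recurrence, but no planned summary or causality step uses their HSV-2 PCR result, so a cream reaction could be attributed to herpes

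*Protocol*

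**What the plan says.** **Recognition and sampling.** Protocol 5.2.6 asks for a swab whenever a suspicious lesion appears: "If a lesion develops that is consistent with genital herpes, swabs should be obtained from the lesion". It describes recurrence by lesion type: "Participants who have such a recurrence (i.e., papules, vesicles or pustules, ulcers, or crusts) during the treatment period". These participants are asked to return for a genital examination. Neither document makes PCR confirmation a condition for calling the episode a recurrence. Appendices 2 and 3 assign a separate red-labelled vial ("If you develop a herpes lesion, please rub a separate swab over this area and place the swab in one of the" red-labelled vials, in the women's version).

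**Testing.** Protocol 9.6 states: "Swab samples will be analyzed by a core laboratory for HSV DNA". The wording is general and would cover lesion swabs. Protocol 10.8 has core-laboratory data entered in the e-CRF for each participant.

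**Analysis.** The only SAP item that names lesion swabs is a compliance question in section 3.6: "Did the participant complete the swab lesion log according protocol". The performance analyses (SAP 1.3 and 4.2) use paired swabs on days of asymptomatic shedding. The lesion summaries in SAP 4.3.2 come from the diary.

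**Adverse events.** SAP 5.2.2 has a row "Recurrence of genital herpes" under complications of HSV-2 infection, not divided by virology. Protocol 8.1.2 names the anticipated device harms as "Toxic, hypersensitive or allergic reaction" and epithelial sensitization.

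**The concern.** The cream goes daily onto the same skin where these participants are expected to have recurrences. A local reaction with papules or erosions could look like herpes. In an HSV-2-seropositive person with a history of recurrences, herpes is the natural first explanation.

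That explanation bears on causality. Under Protocol 7.2 an event is Remote if another cause is more likely, and Possible requires that nothing else reasonably explains it. A clinical diagnosis of herpes can therefore take an event out of the group rated possibly, probably or definitely device-related. The study has a single arm (SAP 1.5), so no control group could reveal an excess of lesions caused by the cream.

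At stake is the description of the nature and causality of adverse events, a secondary endpoint in a trial whose primary objective is safety. The lesion swab is the most direct laboratory evidence on the question, and the plan gives it no stated role.

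**Working it through.** **1. Trace the lesion PCR result through the plan**

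| Step | Place | Is lesion PCR given a role? |
|---|---|---|
| Calling a recurrence | Protocol 5.2.6 | No; lesion type and examination |
| Performance endpoints | SAP 1.3, 4.2 | No; paired swabs on asymptomatic days |
| Lesion summaries | SAP 4.3.2 | No; diary entries |
| Lesion swab item | SAP 3.6 | No; whether the log was completed |
| Recurrence row | SAP 5.2.2 | No split by result |
| AE listing | SAP 5.2.3 | Not named; a general field for diagnostic tests could hold it |
| Causality rating and Safety Officer review | Protocol 7.2 | Not required, not forbidden |

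Timing adds to the gap. Appendices 2 and 3 let participants store swabs at home and bring them to the next appointment. No laboratory turnaround is given, so the result may arrive after causality has been rated. Nothing says the rating is then revisited.

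**2. How many episodes are involved**

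Inputs: 46 participants applying cream and 28 days of sampling (Protocol 9.1); at least 3 recurrences in a year (Protocol 4.1). A rate of 6 a year is an assumption to show the range.

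Expected episodes = participants × yearly rate × 28/365:
- at 3 a year: 46 × 3 × 28/365 = 10.6
- at 6 a year: 46 × 6 × 28/365 = 21.2

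This assumes that past rates continue and that everyone is followed for 28 days. It counts expected recurrences, not misattributed reactions.

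**3. How many reactions could there be**

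The documents give no rate of cream reactions in this population. Protocol 2.3 reports none in 50 exposed subjects. The exact two-sided 95% upper limit for 0/50 is 1 − 0.025^(1/50) = 7.1%, and 46 × 0.071 = 3.3. The earlier study is thus compatible with anything from no reactions to about 3 in 46. It used a different exposure schedule, so this is only a rough guide.

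**4. Does the primary endpoint move**

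The plan's own figure reproduces. With no SADE, the exact upper limit is 1 − 0.025^(1/36) = 9.74%, below 10%; with 35 participants it is 10.00%. Hence 36.

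One SADE would break the rule at any planned size: the upper limit is 14.5% for 1/36, 12.6% for 1/42 and 11.5% for 1/46. A lesion counts here only if it is both device-related and serious under Protocol 7.1, which a local skin reaction would not usually be.

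**The case against.** A reader might infer that a cream reaction resembling herpes will be tabulated as HSV-2 disease instead of as a device effect. The documents do not support that. SAP 5.2.2 tabulates the same events in parallel as toxic, allergic, infectious or other, by device relatedness, and as HSV-2 complications. Nothing makes these views exclusive, and no rule assigns every lesion to the recurrence row.

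Nor is it safe to say that no listing could show the result. SAP 5.2.3 lists diagnostic tests and their results beside causality for every event. SAP 5.3.1.3 adds a similar listing for events that led to an intervention, and many recurrences would qualify.

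Other evidence also informs attribution. Participants are examined, SAP 3.6 separates new abnormalities related to herpes from those that are not, and the Safety Officer reviews all adverse events.

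PCR is not a clean discriminator either. The plan anticipates asymptomatic shedding at a rate of 8% (Protocol 9.1), and Protocol 1.2.2 cites up to 25% of days, so a reaction can coincide with shedding and test positive. A healing herpes lesion can test negative.

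All of this stands, and it limits the point to a risk of misattribution. It does not close the gap: a general field in a line listing neither summarises recurrences by result nor ensures that the result is seen when causality is judged.

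**Conclusion.** The point holds as a modest gap in the safety analysis. Lesion swabs are collected and fall under the core-laboratory testing, but no SAP summary uses their PCR result, and neither the causality rating nor its review is tied to it. A PCR-negative lesion on treated skin could be called a recurrence, rated Remote, and drop out of the device-related table.

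The row concerned should contain about 11 to 21 episodes, on the assumptions of 46 participants, 28 days and 3 to 6 recurrences a year. How many would be misattributed cannot be estimated from the documents. It would be wrong to conclude that device effects will be under-counted; they could be. The effect is on the secondary safety endpoint. The primary SADE endpoint is touched only by a serious event, and no stated sample size changes. The change is worth making because it is cheap and uses data already collected.

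**What to change.** Three changes to the SAP:

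1. **Section 5.2.2.** Split the recurrence row into lesion swab HSV-2 DNA positive, HSV-2 DNA negative, and not swabbed or no result. Cross-tabulate the three with device causality.
2. **Section 5.2.3.** State that the lesion PCR result is shown in the existing field for diagnostic tests.
3. **Before database lock.** Have the Safety Officer, who already reviews all adverse events, look again at the device causality of PCR-negative episodes with the result in hand, and record the outcome. A negative result should not relabel an event automatically.

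The cost is SAP wording, one table split and one short review round. Swabs, lesion log and core laboratory are already in place. Sample size, sampling and patient management do not change. The downside is that PCR errs in both directions, so some episodes will stay unresolved and should be reported as such.
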